1 PURPOSE

This document describes the planned statistical strategies for the analysis of data for the "Pharmaceutical Interventions for Noise-Induced Hearing Loss—Acute Exposure Treatment (PINIHL-AET)" Study. The document will be shared with the members of the Data Safety Monitoring Board (DSMB) and will be modified based on their feedback and requests.

Data reports will be prepared for the DSMB and will be part of the DSM report that will be prepared by the study team with assistance from the study statistician. The DSM report will be prepared for the DSMB semi-annually and at other times at the discretion of the DSMB. The DSM report will be reviewed by the DSMB, and will be submitted to the PI. The DSMB must meet at least every six months beginning six months after study activation at Washington University beginning six months after enrollment of the first patient at the secondary site, or due to Adverse Events (AE) or Serious Adverse Events (SAEs) to ensure subject safety through data, process or conduct of study and recommend to the sponsor on continuation, modification, or termination of the study, and no more than one month prior to the due date of the DSM report to the PI.

In the event of future amendments to the protocol, this SAP will be modified as necessary to account for changes relevant to the statistical analysis.

1.1 RESPONSIBLITIES

Pharm-Olam will perform the statistical analyses and is responsible for the production and quality control of all derived datasets and tables, listings, and figures.

2 INTRODUCTION

2.1 STUDY DESIGN

This study is a randomized, double-blinded, placebo-controlled trial with three parallel groups, to make use of a common control group between the experimental groups. Subjects will be randomized in a balanced fashion into one of 3 arms: Zonisamide (ZNS) pre-op, Placebo, or ZNS post-op.

Study Subjects will be recruited from the Washington University Otology clinics. Patients will be offered participation if they are undergoing skull-based surgery as part of their standard treatment. These are patients that would be recommended skull-based surgery despite this investigation and this investigation will have no influence on treatment recommendations.

Figure 1 Overall Study Design

2.2 STUDY OBJECTIVES

2.2.1 Primary Objective

To determine if preoperative and/or postoperative ZNS is more effective than placebo at preventing a permanent threshold shift (PTS) in the contralateral ear of patients undergoing drilling during skull base surgery.

The primary efficacy outcome will be the proportion of PTS-positive subjects defined as the ratio of PTS-positive subjects to total number of subjects in each study arm/group. PTS positive will be defined as all subjects who in audiogram are identified as having a PTS of \geq 10 dB HL increase at any frequency between 2-6 kHz post-surgery as compared to baseline audiogram.

2.2.2 Secondary Objectives

To determine if preoperative and/or postoperative ZNS is more effective than placebo at preventing a temporary threshold shift (TTS), synaptopathy, and degraded speech perception in the contralateral ear of patients undergoing drilling during skull base surgery.

2.2.3 Exploratory Analysis

To identify a genetic risk profile associated with drilling-induced hearing loss we will survey known genetic markers associated with NIHL including markers in CDH23, PCDH15, EYA4, MYO1A, KCNMA1 and OTOG1 and zonisamide (ZNS) metabolism, CYP2C9 and CYP2C192. If significant associations are observed and validated in a subsequent clinical study, we will optimize drug dosages based on a subject's genetic profile.

2.3 Study Population

We plan to enroll approximately 234 subjects over approximately 4 years. Subjects will be randomized in a balanced fashion into one of the 3 arms: ZNS 100 mg pre-op, Placebo, or ZNS 100 mg post-op. We proposed the three-group design in order to establish a common control group between the experimental groups. Enrolled study subjects will be randomized into three equal groups. The placebo group is the common group for comparison to each active group independently. Alpha error will be adjusted for multiple comparison.

2.4 Randomisation

Eligible subjects will be randomized in a balanced fashion into one of the 3 arms: ZNS 100 mg pre-op, Placebo, or ZNS 100 mg post-op. To balance noise-exposure history across study arms we will employ stratified randomization. The subjects will be stratified based on noise exposure survey responses (see table below), and will then be randomized to study groups. Randomization will be based on the randomization list generated by unblinded statistician using a computer algorithm written in SAS® using randomly selected blocks of sizes 3. Within each block of 3, there will be 1 subject assigned to each study group. The random assignment of subjects to the different study groups will be associated with consecutively assigned random numbers which will be unique for each study subject. The stratified kit list will be provided to Advanced Rx who will package and label the drug for shipment to the pharmacist. Each kit will contain two bottles and will be labeled with the same kit number. The bottle will not contain any information of the treatment allocation. One interim analysis is planned, once 33% (n=78) of the subjects have completed participation in the study.

Name	Description
1: High Noise	Screening: LENS-Q Adapted for Surgical Noise Study – 1A Or 2A Or 4A = a.Daily, Or b.Less than daily/more than weekly, Or c.Weekly, Or d.Less than weekly/more than monthly Or e.Monthly OR 1C Or 2C Or 3C >= 5 Years

Name	Description
2: Low Noise	Screening: LENS-Q Adapted for Surgical Noise Study – 1A AND 2A AND 4A = f.Less than monthly/more than yearly, g.Yearly, h.Less than yearly Or i.Never OR 1C AND 2C AND 3C < 5 Years

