The study will be "masked" or "blinded" in the sense that all the study participants and the study team members will be blinded to the assignment in the study groups. Only the pharmacist who will prepare the study drug kits and the unblinded Statistician will have access to the kit assignments. A copy of the randomization kit list with study ID assignments will be saved in a limited access folder on a secure network server at Pharm-Olam. The Medical Monitor will be contacted in emergent medical cases when knowing the treatments assignment is mandatory for clinical care of the patient.

At the time when we will need to "freeze" the data sets for purposes of developing the DSMB report, a series of SAS programs will be run from an independent programmer to produce data for each pairwise comparison into two subsets of data from the total cohort. Each subset will be de-identified. A previously prepared SAS code will be run in each subset and the output will be used to complete the table shells where the groups will not be identified. The programmer preparing subsets will not be involved in the handling of data forms or the analysis of data.

Study participants will be recruited from the Washington University Otology clinics. Patients will be offered participation if they are being offered skull-based surgery as part of their standard treatment. These are patients that would be recommended skull-based surgery despite this investigation and this investigation will have no influence on treatment recommendations. Consenting and eligible participants will be scheduled for standard of care surgery.

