#### 5.2 Randomization

Participants will be randomized into one of three groups as shown below:

	Pre-op Package	Post-op Package
Pre-op group	ZNS 100 mg PO	Placebo
Placebo group	Placebo	Placebo
Post-op group	Placebo	ZNS 100 mg PO

Randomization will be based on a randomization list generated by unblinded statistician using a computer algorithm written in SAS using randomly selected blocks of sizes 3. Within each block of 3, there will be 1 subject assigned to each study group. To balance noise-exposure history across study arms we will employ stratified randomization. The subjects will be stratified based on noise exposure survey responses (see table below), and will then be randomized to study groups. The random assignment of subjects to the different study groups will be associated with consecutively assigned random numbers which will be unique for each study participant. The stratified kit list will be provided to Advanced Rx who will package and label the drug for shipment to the pharmacist. Each kit will contain two bottles and will be labeled with the same kit number. The bottle will not contain any information of the treatment allocation. One interim analysis is planned, once 33% (n=78) of the subjects have completed participation in the study.

Study medication will be dispensed to the participants with instruction to take their first assigned dose prior to surgery. Participants will take their second assigned dose within 12 hours after surgery or when the patient is released clinically to oral medication. Participants will be instructed to take zonisamide without food. We will recommend that capsules be swallowed whole per the current approved labeling.

Name	Description
1. High Noise	Screening: LENS-Q Adapted for Surgical Noise Study –

Name	Description
	a.Daily, Or b.Less than daily/more than weekly, Or c.Weekly, Or d.Less than weekly/more than monthly Or e.Monthly OR 1C Or 2C Or 3C >= 5 Years
2: Low Noise	Screening: LENS-Q Adapted for Surgical Noise Study –  1A AND 2A AND 4A = f.Less than monthly/more than yearly, g.Yearly, h.Less than yearly Or i.Never  OR  1C AND 2C AND 3C < 5 Years

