2.5 Treatment Assignment and Blinding

To ensure double-blinding of the trial, each subject will be randomized to one of three treatment arms via an interactive randomization tool (IRT) and assigned to a study group. Once randomized, each subject will be provided a kit on the day of surgery that contains two bottles, with one package labeled to be taken prior to surgery, and another package designated to be taken within 12 hours after surgery or when patient is released clinically to oral medication. For subjects randomized to "ZNS pre-op", the pre-op package will contain one ZNS capsule of 100 mg, and the post-op package will contain one placebo capsule that looks and tastes the same as ZNS capsules. For subjects randomized to "ZNS post-op", the pre-op package will contain one placebo capsule and the post-op package will contain one ZNS capsule of 100 mg. For the subjects randomized to "placebo", both pre- and post-op packages will contain capsules of placebo.

The study will be "masked" or "blinded" in the sense that all the study subjects and the study team members will be blinded to the assignment in the study groups. Only the pharmacist who will prepare the study drug kits and the unblinded Statistician will have access to the kit assignments. A copy of the randomization kit list with study ID assignments will be saved in a limited access folder on a secure network server at Pharm-Olam. The Medical Monitor will be contacted in emergent medical cases when knowing the treatments assignment is mandatory for clinical care of the patient.

At the time when we will need to "freeze" the data sets for purposes of developing the DSMB report, a series of SAS programs will be run from an independent programmer to produce data for each pairwise comparison into two subsets of data from the total cohort. Each subset will be de-identified. A previously prepared SAS code will be run in each subset and the output will be used to complete the table shells. Table shells will be blinded. If DSMB members find any safety issues, they may request specific unblinded data. The programmer preparing subsets will not be involved in the handling of data forms or the analysis of data. Table shells for DSMB (content and formats) will be agreed upon prior to start of study.

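### One fixed, disclosed block size of 3: unblinding a placebo patient would expose both block partners as ZNS, provided the block can be reconstructed

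*SAP*

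**What the plan says.** Three arms are allocated in equal numbers: "ZNS 100 mg pre-op, Placebo, or ZNS 100 mg post-op" (SAP 2.4). Both documents give one block size. SAP 2.4 has the list made "using randomly selected blocks of sizes 3. Within each block of 3, there will be 1 subject assigned to each study group"; Protocol 5.2 has the same rule, "using randomly selected blocks of sizes 3", and adds "Within each block of 3, there will be 1 subject assigned to each study group". No other size appears, and neither document says that the size is kept from the site.

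Allocation is stratified by noise history, high or low: "The subjects will be stratified based on noise exposure survey responses (see table below), and will then be randomized to study groups" (SAP 2.4). Assignments are "associated with consecutively assigned random numbers which will be unique for each study subject". Protocol 4.0 names one source of patients: "Study participants will be recruited from the Washington University Otology clinics". Secondary sites appear in the reporting rules (Protocol 8.1.3 and 8.2), and adding sites is a contingency if enrolment is slow (Protocol 12.4, SAP 4.4).

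Both documents foresee that a single patient may be unblinded:

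- SAP 2.5 (and Protocol 4.0): "The Medical Monitor will be contacted in emergent medical cases when knowing the treatments assignment is mandatory for clinical care of the patient".
- Protocol 8.0: after a serious adverse event for which the PI judges it necessary, the assignment goes to the doctor treating that patient.
- Protocol 12.4 and SAP 8.1.1: the DSMB may break the blind when it assesses serious adverse events. SAP 2.5 also lets it request unblinded data.

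**The concern.** With exactly one patient per arm in each block, one known assignment removes that arm for the two partners. Three is the smallest block possible for three equal arms, so it gives away the most. Because the size is fixed and printed, anyone who knows the order of enrolment within a stratum could count off blocks in threes, if the list is used in sequence.

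What is at stake is the blind of patients who were never themselves unblinded. The primary endpoint rests on a behavioural test in which the participant presses a button (Protocol 5.1). A shift of 10 dB or more at a single frequency from 2 to 6 kHz makes a patient PTS-positive (SAP 3.2). The test is at day 30, after any peri-operative unblinding. Beyond the general statement that participants and study team are blinded, I found no separate arrangement for the person who runs the audiogram.

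**Working it through.** **Inputs.** From the documents: block size 3, one patient per arm, three arms of which two contain ZNS, two strata, 78 per arm, 234 in total. Assumed, because the documents give no figure: unblinding of 2% to 5% of patients, independent of arm. Block sizes 6 and 9 are illustrative comparators.

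**The plan's own figures.** 3 × 78 = 234, which is 234 / 3 = 78 blocks if all are filled. The stated 80.4% power (50% versus 25%, one-sided 0.0125) also reproduces: exact enumeration of Fisher's test gives 80.7%, and an arcsine approximation with continuity correction gives 80.4%. Neither depends on block size.

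**Placebo patient unblinded, block membership known.** Of the 6 orderings of a block of 3, 2 put placebo in a given position. In both, the other two patients are one pre-op ZNS and one post-op ZNS, so both are on ZNS with probability 2/2 = 100%. Which of them is pre-op stays 50/50. For a block of size b:

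- one named partner on ZNS: (2b/3) / (b − 1)
- two named partners both on ZNS: the above × (2b/3 − 1) / (b − 2)

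| Block size | One partner on ZNS | Two partners both on ZNS |
|---|---|---|
| 3 | 2/2 = 100% | 100% |
| 6 | 4/5 = 80% | 0.80 × 3/4 = 60% |
| 9 | 6/8 = 75% | 0.75 × 5/7 = 53.6% |
| no blocking | 2/3 = 66.7% | 4/9 = 44.4% |

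**Placebo patient unblinded, block boundary unknown.** If the patient is first or second in the block, the next patient in the stratum is on ZNS for certain. If third, the next patient opens a new block and is on ZNS with probability 2/3. The average is (1 + 1 + 2/3) / 3 = 88.9%, against 66.7% with no information.

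**ZNS patient unblinded.** The two partners are one placebo and one on the other ZNS arm, so each has probability 1/2 of ZNS, down from 2/3. If two members of a block are unblinded, the third is fixed.

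**How many patients.** One third of those unblinded are taken to be on placebo, and each has two partners.

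| Unblinded | Patients | Partners revealed as ZNS | Partners narrowed to 50% |
|---|---|---|---|
| 2% | 234 × 0.02 = 4.68 | 4.68 × 1/3 × 2 = 3.1 | 4.68 × 2/3 × 2 = 6.2 |
| 5% | 234 × 0.05 = 11.7 | 11.7 × 1/3 × 2 = 7.8 | 11.7 × 2/3 × 2 = 15.6 |

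These are upper bounds. They assume full blocks, every unblinded patient in a different block, and every block reconstructed.

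**The case against.** The block inference is only the first link. No passage sends an assignment to the audiology tester or to another participant. Under Protocol 8.0 the PI decides that unblinding is needed, but the assignment goes to the treating doctor; the DSMB is independent. For the endpoint to be biased, the information must leave that circle, someone must reconstruct the block, the tester or partner must learn of it, and a day-30 threshold must change as a result. That stands, and it limits how often harm could occur.

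Block membership is also not handed to the site. Assignment runs through an interactive randomisation tool (Protocol 4.0, SAP 2.5), and the documents do not say how kit numbers map to blocks. If sites were added, no single site need see the whole order within a stratum, because stratification is by noise history only. A reader might infer that unblinding any placebo patient exposes the partners with certainty. The documents do not support that without known membership. The counter-argument is that scrambled kit numbers alone would not protect: the inference uses order within stratum, and one institution that scores the stratum itself can probably follow that order.

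A reader might also add revealed and narrowed partners together and conclude that about 9 to 23 patients, up to 10% of the trial, lose their blind. Only the partners of placebo patients are revealed, about one third of that total.

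Finally, the phrase about random selection can be read as a random choice among the six orderings. On that reading the sentence is not an error, but it still leaves one block size.

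**Conclusion.** The weakness is real but conditional: a cheap improvement rather than a flaw that undermines the primary comparison. Exposure of both partners as ZNS requires an unblinded placebo patient and a block that can be reconstructed. With the boundary unknown, the inference weakens to 88.9% for the next patient in the stratum. At the assumed 2% to 5% unblinding, about 3 to 8 partners (at most 7.8 / 234 = 3.3% of the trial) would be revealed, and about 6 to 16 more would be narrowed.

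It would go too far to infer that the audiogram results will be biased or the type I error inflated. Nothing in the documents shows the information reaching the tester or the participant, and no effect on the PTS proportions has been calculated. Nor can the next allocation be predicted from block size alone: capsules are matched, so some assignment must first become known.

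**What to change.** In Protocol 5.2 and SAP 2.4, replace the block sentence with: *permuted blocks of randomly varying size, 1:1:1 within stratum*. Hold the sizes (for example a random mix of 3, 6 and 9) only in the unblinded statistician's restricted specification, and regenerate the list for kits not yet allocated. SAP 8.4 describes screening ECGs under earlier protocol versions in the past tense, so recruitment may already have started. For patients already allocated, the printed size cannot be withdrawn.

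The cost is an update of the unused part of the stratified kit list, with the packager, and of the randomisation tool. If the list has been partly used, the trial will have two list-generation schemes to document. With blocks of up to 9, the between-arm difference within a stratum at any moment can reach 3 instead of 1. Over two strata that is at most 2 × 3 = 6 instead of 2 × 1 = 2, so balance at the interim planned with 26 per group would be slightly less exact. The planned sample size, power and analysis do not change.

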2.5 Treatment Assignment and Blinding

To ensure double-blinding of the trial, each subject will be randomized to one of three treatment arms via an interactive randomization tool (IRT) and assigned to a study group. Once randomized, each subject will be provided a kit on the day of surgery that contains two bottles, with one package labeled to be taken prior to surgery, and another package designated to be taken within 12 hours after surgery or when patient is released clinically to oral medication. For subjects randomized to "ZNS pre-op", the pre-op package will contain one ZNS capsule of 100 mg, and the post-op package will contain one placebo capsule that looks and tastes the same as ZNS capsules. For subjects randomized to "ZNS post-op", the pre-op package will contain one placebo capsule and the post-op package will contain one ZNS capsule of 100 mg. For the subjects randomized to "placebo", both pre- and post-op packages will contain capsules of placebo.

The study will be "masked" or "blinded" in the sense that all the study subjects and the study team members will be blinded to the assignment in the study groups. Only the pharmacist who will prepare the study drug kits and the unblinded Statistician will have access to the kit assignments. A copy of the randomization kit list with study ID assignments will be saved in a limited access folder on a secure network server at Pharm-Olam. The Medical Monitor will be contacted in emergent medical cases when knowing the treatments assignment is mandatory for clinical care of the patient.

At the time when we will need to "freeze" the data sets for purposes of developing the DSMB report, a series of SAS programs will be run from an independent programmer to produce data for each pairwise comparison into two subsets of data from the total cohort. Each subset will be de-identified. A previously prepared SAS code will be run in each subset and the output will be used to complete the table shells. Table shells will be blinded. If DSMB members find any safety issues, they may request specific unblinded data. The programmer preparing subsets will not be involved in the handling of data forms or the analysis of data. Table shells for DSMB (content and formats) will be agreed upon prior to start of study.

2.6 Schedule of Assessments and Procedures

Table below summarizes the calendar of study activities and assessments

	Screening / Baseline	Surgery	Post-op	
	Within 30 days (+3 days) prior to surgery		Within 12 Hours	Within 30 days (+/- 3 days)
Informed consent	X			
Clinical Exam	X			
Demographic Info	X			
Pre-Op Data (pregnancy test, lab results (electrolyte panel, BUN, Cr, ALT, and AST)	X			
Current Meds	X			
Questionnaire	X			X
Audiogram	X			X
ECochG	X			X
DPOAE	X		X*	X
WIN	X			X
Randomization	X			
Oral Dose**		X	X	
Blood draw***			X	
AE assessment		X	X	X

^{*} Within 8 hours

2.7 Sample Size Determination for The Primary Efficacy Outcome Measure

The primary efficacy outcome will be the proportion of PTS positive subjects defined as the ratio of PTS-positive subjects to total number of subjects in each study arm/group. Using pilot data from a retrospective chart review of 75 similar patients undergoing \geq 1-hour drill noise exposure, we estimate the proportion of PTS positive subjects in the placebo group will be 50%. We hypothesize that the expected effect of ZNS either pre-op or post-op will be a 50% reduction of the proportion of subjects with PTS positive as compared to placebo group. This is the desired clinically significant effect for treating hearing loss for single dose of 100 mg ZNS.

The sample size for this study was calculated for the planned comparisons of each of the ZNS groups with the placebo group using a balanced design and a one-sided alpha level of 0.0125 Based on the data from our retrospective study, using Fisher's exact test we estimated that 78 subjects in the ZNS group and 78 subjects in the placebo group will be needed to provide us with 80.4 % power to detect a 50% reduction in the proportion of PTS positive subjects *(from 50% to*

^{**}Dispensed on the day of surgery with instruction to take first dose prior to surgery and second dose after surgery.

^{***} Plasma sample for PGx will be collected at baseline visit. Plasma sample for ZNS level and PGx, electrolyte panel, BUN, Cr, ALT, and AST will be collected 12 hours after first dose.

25% corresponding to an absolute proportion difference of 25%) at the 1-sided alpha level of 0.0125 for each ZNS-Placebo group comparison. A total of 234 subjects will be enrolled to be randomized in this study. All efforts will be made minimize and eliminate drop outs. Given the short term-follow-up of study subjects in a period where they are under medical care, few, if any, drop-outs or lost to follow-up are expected.

Sample size calculations were carried out using PROC POWER procedure in SAS 9.4.

3 Study Outcomes

